2.3.6 Pharmacodynamic Assessments

Blood samples will be collected on Day 1, and Weeks 1, 2, 4, 12, 20, 26, 28, 32, 38, 52, 54, 57 and 60 for PD marker measurements in plasma and serum, which may include, for example, cystatin C, complement components, and inflammatory cytokine and chemokine levels. Blood samples collected will be used for lymphocyte subset counts including B cells, T cells, and natural killer cells. The complete blood cell (CBC) count results from the hematology samples will also be included in the PD assessments. The PK plasma samples may also be used for PD marker measurements.

Urine samples will be collected according to the same schedule as for blood samples with the exception of Weeks 54 and 57 for biomarker assessments including, for example, soluble CD163, complement fragments, and inflammatory cytokine and chemokine levels.

Details of the PK and PD analysis will be described in a separate analysis plan and will be reported in a separate report.

2.3.7 Safety Endpoints

2.3.7.1 Adverse Events

Safety endpoints include subject incidence of treatment-emergent serious adverse events, treatment emergent non-serious adverse events, and withdrawals from the study drug or clinical trial due to adverse events.

An adverse event will be considered treatment-emergent (TEAE) if the start date of the event is on or after the date of administration of the first dose of study medication. All reported adverse events will be classified by system organ class and preferred term using the Medical Dictionary for Regulatory Activities (MedDRA) (version 19.1). Treatment-emergence will also be determined based on the Safety Populations defined in Section 3.2.3.

The relationship to avacopan/placebo will be determined by the Investigator. The sponsor will perform a safety analysis based on an aggregate analysis across the safety database as well as the assessment of individual cases of interest.

A serious adverse event (SAE) is defined as any untoward medical occurrence that at any dose results in death, is life-threatening, requires or prolongs hospitalization, results in persistent or significant disability or incapacity, is a congenital anomaly or birth defect, or is an important and significant medical event that, based on appropriate medical judgment, may jeopardize the subject and/or may require medical or surgical intervention to prevent one of the other outcomes defining serious.

In addition, specific TEAEs of interest will be presented by treatment group (see Section 6.3).

2.3.7.2 Clinical Laboratory Assessments

Safety endpoints related to clinical laboratory assessments include change from baseline and shifts from baseline in all safety laboratory parameters, including blood chemistry, hematology, and urinalysis.

Clinical laboratory assessments will be performed at the visits identified in the Time and Events Table in the protocol:

- Hematology: hemoglobin, hematocrit, red blood cell (RBC) count, white blood cell (WBC) count with differential, platelet count, mean cell hemoglobin, mean cell hemoglobin concentration, mean corpuscular volume
- Serum Chemistry: liver panel (total and fractionated bilirubin, lactate dehydrogenase, aspartate aminotransferase, alanine aminotransferase, alkaline phosphatase), renal panel (blood urea nitrogen, creatinine), creatine phosphokinase (CPK), albumin, sodium, potassium, magnesium, bicarbonate, chloride, calcium, inorganic phosphorus, glucose, total protein, alkaline phosphatase, total cholesterol, uric acid, serum amylase, and serum lipase
- Coagulation: Prothrombin time (PT) and International normalize ratio (INR) if retest is performed because of ALT and/or AST >3x ULN

- Urinalysis: At the central laboratory, blood, nitrite, and protein, will be tested. If positive for blood, nitrite or protein, microscopy examination will be performed
- Virology (measured only at screening and may be measured at the local laboratory): hepatitis B surface antigen, hepatitis C antibodies, HIV 1 and 2 antibodies; virology tests done within 6 weeks prior to screening are acceptable for eligibility assessment. Results from prior tests performed at the local laboratory must be recorded in the EDC system
- TB screen: only one of the following is needed: interferon γ release assay (IGRA), tuberculin purified protein derivative (PPD) skin test, or chest radiograms (X rays or CT scan); chest radiography done within 6 weeks prior to screening is allowed for eligibility assessment

Specific laboratory abnormalities that would prompt pausing or permanently discontinuing study drug (avacopan or placebo) including white blood cell count, neutrophil count, lymphocyte count, AST or ALT and other lab abnormalities of impaired liver function of hepatic toxicity, CPK increase, creatinine or proteinuria increase may be summarized.

2.3.7.3 Complement Panel

The following panel will be measured in all subjects at baseline based on recommendations from a consensus panel (Pickering et al., 2013):

- Plasma C3a, C5a, C5b-9, and C5;
- Serum C3 and C4;
- Serum C3 nephritic factor;
- Plasma complement factor H and factor B;
- Serum factor H auto-antibody;
- Serum paraprotein detection;
- CFHR5 mutation

Results from tests performed within 4 weeks prior to screening will be allowed for the study. For CFHR5 mutation, results from tests performed any time in the past will be allowed. If these tests have not been performed previously in a subject, samples need to be collected prior to Day 1 for measurement either at the local laboratory (if capabilities exist) or at the central laboratory. Results from these tests do not need to be available prior to start of dosing on Day 1, except for C5b-9 which is needed for eligibility assessment. Results from tests performed at the local laboratories need to be recorded in the EDC.

2.3.7.4 Vital Signs

Individual vital sign values including temperature, blood pressure and heart rate, and change from baseline will be calculated. Visits to be listed and summarized include Screening, Day 1, and Weeks 1, 2, 4, 8, 12, 16, 20, 26, 28, 32, 38, 44 and 52 during the treatment period and Weeks 54, 57 and 60 during the follow-up.

Height and weight are to be measured as part of the vital signs. Height is to be recorded at screening only, except for adolescents (12-17 years old) in whom height is also to be included as part of all vital signs. Body mass index (BMI) will be calculated from the body weight and

height measurements. Height, weight and BMI will be listed and weight and BMI will be summarized.

2.3.7.5 ECG

ECG Interpretation (normal/abnormal), clinical significance (yes/no) and description of abnormality will be listed. Visits to be listed include Screening, Day 1, and Weeks 1, 26, 28, 32 and 52 during the treatment period and Weeks 54, 57 and 60 during the follow-up. Clinically significant findings at screening should be reported as Medical History and abnormal changes compared to baseline should be recorded as adverse events as appropriate.

2.3.7.6 Physical Exam

A complete physical examination (including evaluation of general appearance/mental status, HEENT [head, eyes, ears, nose, throat], and the following body systems: dermatologic, cardiovascular, respiratory, gastrointestinal, musculoskeletal and neurologic) for safety will be performed at Screening, Day 1, Weeks 1, 2, 4, 8, 12, 16, 20, 26, 28, 32, 38, 44 and 52 during the treatment period and Weeks 54, 57 and 60 during the follow-up. Overall assessment (normal/abnormal) and clinical significance (yes/no) will be listed. Clinically significant findings should be reflected in Medical History or recorded as adverse events as appropriate.

3 STATISTICAL METHODOLOGY

3.1 General Considerations

For efficacy analysis, to control for the Type I error rate, a gate-keeping procedure will be applied for the analysis of the primary efficacy endpoint (percent change in C3G Histologic Index for disease activity). The primary endpoint will be tested in the elevated C5b-9 stratum first with a two-sided $\alpha = 0.05$. If this test reaches statistical significance, then the primary endpoint will be tested in the combined C5b-9 strata (including both elevated and non-elevated C5b-9 strata) with a two-sided $\alpha = 0.05$. If the test in the elevated stratum fails to reach statistical significance, then the test in the combined C5b-9 strata will only be performed as an exploratory analysis. The statistical analysis for the secondary endpoint (C3G Histologic Index for disease chronicity) will be tested at a 0.05 α -level only if the primary endpoint in the same stratum reaches statistical significance.

Data will be summarized descriptively by treatment group as well as separately for the elevated C5b-9 stratum and combined strata. For continuous variables, numbers, means, medians, ranges, standard deviations, and standard error of means will be calculated. Geometric means will be calculated for UACR and urinary MCP-1:creatinine ratio, and other data that are not normally distributed. Frequency counts and percentages will be presented for categorical variables. Listings of raw and derived data will be included as part of an appendix to the CSR.

In analysis tables and listings, the two treatment groups will be referred to as

- 'Placebo', referenced in the protocol as Group A (placebo)
- 'Avacopan', referenced in the protocol as Group B (avacopan)

3.1.1 Study Day

Study day or analysis day will be calculated from the date of first dose of study drug. The day of the first dose of study drug will be Day 1, and the day immediately before will be Day -1. There will be no Day 0.

3.1.2 Analysis Visits for Efficacy

Scheduled visits will be assigned to analysis visits as recorded in the EDC system. If a scheduled visit is not available, unscheduled and early termination visits will be assigned to analysis visits using analysis visit windows based on the actual date the assessment took place. The start day of the analysis window will be calculated as the midpoint between the scheduled assessment and previously scheduled assessment for that parameter. The end day of the analysis window will be calculated as the midpoint between the scheduled assessment and the next scheduled assessment for that parameter. Where multiple measurements for a particular parameter appear within an analysis visit, the scheduled visit will be used. If no scheduled visit appears in the analysis window, the result closest to the target day will be used. If equidistant and both are unscheduled and/or early termination visits, the later result will be used for the summary measure. Note that scheduled visits may appear outside of the analysis day window due to factors such as COVID-19 and related factors which could have limited the ability for subjects to visit the study site. Due to specific study procedures performed at these visits, the scheduled study visit will be used in these cases. Individual adjustments may be made for subsequent unscheduled or early termination visits that occur after this visit should they appear in an analysis day window prior to the scheduled visit.

Though all measures may not be used in data summaries (e.g., two lab measures within the same analysis visit window), all measurements appear in the datasets and listings. For subjects where the event date is missing, the study day and analysis window will also be missing. See the following table for an example of analysis windows.

Analysis Visit	Analysis Day Target	Analysis Day Window [1]
Week 1	8	2 - 11
Week 2	15	12 - 22
Week 4	29	23 - 43
Week 8	57	44 - 71
Week 12	85	72 - 99
Week 16	113	100 - 127
Week 20	141	128 - 152
Week 23	162	153 - 173
Week 26	183	174 - 190
Week 28	197	191 - 211
Week 32	225	212 - 236
Week 35	246	237 - 257
Week 38	267	258 - 278
Week 41	288	279 - 299
Week 44	309	300 - 323
Week 48	337	324 - 351

Analysis Visit	Analysis Day Target	Analysis Day Window [1]
Week 52	365	352 - 372

[1] Scheduled visits are being used when available and may appear outside of the analysis day window due to factors such as COVID-19 and related factors which could have limited the ability for subjects to visit the study site

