3.2. Randomization

Patients will be randomized using an interactive response technology (IRT) system and a minimization algorithm, using the stratification factors, in a 1:1 ratio to one of two treatment groups:

Group A: avacopan-matching placebo twice daily

Group B: avacopan 30 mg twice daily

The earliest timepoint at which the primary efficacy analysis can occur is when the last enrolled patient in the primary population (patients in the elevated C5b-9 stratum, see [Section 8.2.1](#)) has completed the Week 26 visit. After the 26-week double-blind period, the avacopan group will continue receiving avacopan for another 26 weeks, and the avacopan-matching placebo group will be switched over in a blinded manner to receive 30 mg avacopan twice daily treatment, instead of avacopan-matching placebo, for another 26 weeks.

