6.11. Study Week 26 (Day 183)

The Study Week 26 visit must occur within ± 7 days of the scheduled date. During this visit, the following study procedures will be performed:

- A physical examination including body weight; height will also be measured in 12 to 17 year-old patients;
- Vital signs (temperature, sitting blood pressure, heart rate) after at least 3 minutes of rest;
- A 12-lead ECG will be performed after at least 3 minutes of rest in a supine position;
- Blood samples will be collected before the morning dose for shipment to the central laboratory for a serum pregnancy test (in women of childbearing potential), serum chemistry, hematology, lymphocyte subset analysis, and PK and PD measurements. Record the date and time of blood draw;
- The date and time of the last dose of avacopan/ avacopan-matching placebo prior to collection of the PK sample will be recorded;
- The patient will be asked to take the morning dose of avacopan while at the study center;
- The time of the dosing of avacopan will be recorded;
- If the patient is 12 to 17 years old, blood samples will be taken before dosing and at Hour 0.5, 1, 2, 3, 4, and 6 after the morning dose of avacopan; plasma samples will be frozen and sent to the central laboratory for expeditious measurement of avacopan and metabolite plasma concentrations. *Note: it is important that on Day 183 the adolescent patients take the dose when instructed at the study center, NOT at home, and they should be reminded through a telephone call two days before the Day 183 visit.*
- A clean catch, midstream urine sample will be collected for urinalysis, for PD assessment, and for urine protein, urine albumin, urinary MCP-1 and urine creatinine measurement for calculation of UPCR, UACR and urinary MCP-1:creatinine ratio; the sample will be sent to the central laboratory;
- Renal biopsy, performed within -2 weeks prior to the Week 26 visit and BEFORE patient is started on open-label treatment;
- Patients will be asked to complete the SF-36 v2 and EQ-5D-5L;
- Drug accountability will be performed on the returned avacopan/ avacopan-matching placebo bottles;
- Two new bottles of avacopan will be dispensed;
- For adolescents, two new bottles of avacopan will be provided to the patient with dosing instructions according to body weight (see [Section 5.3](#));

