6.23. Early Termination Visit

If a patient is withdrawn early from the study, the following termination procedures must be completed whenever possible:

- A physical examination including body weight; height will also be measured in 12 to 17 year-old patients;
- Vital signs (temperature, sitting blood pressure, heart rate) after at least 3 minutes of rest;
- A 12-lead ECG will be performed after at least 3 minutes of rest in a supine position;
- Blood samples will be collected for shipment to the central laboratory for serum chemistry, hematology, lymphocyte subset analysis and serum pregnancy test (in women of childbearing potential) measurement. Record the date and time of blood draw;
- A clean catch, midstream urine sample will be collected for urinalysis at the central laboratory;
- Drug accountability will be performed on the returned avacopan/avacopan-matching placebo bottles;
- Any changes in concomitant medication use will be recorded, including alcohol intake, recreational drug use, non-prescription medications, herbal preparations or special diets;
- Any adverse events will be recorded. If an adverse event remains unresolved at the conclusion of the study, a clinical assessment will be made by the Investigator and the Sponsor's Medical Monitor to determine whether continued follow-up of the adverse event is warranted.
- A follow-up renal biopsy will be performed if a patient is withdrawn early from the study.

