3.1.8 Adjustments for Potential Impact of COVID-19

COVID-19 pandemic may impact the conduct of the study from different aspects including quarantines, site closures, travel limitations, interruptions to the supply chain for the investigational product, or other considerations if site personnel or trial subjects become infected with COVID-19.

Data fields to capture visit impact due to COVID-19 were added to the database including visit status (visit not completed/in-person visit partially completed/performed virtually), if visit status was due to COVID-19, whether the visit was completed outside of window due to COVID-19 and how or why participation was impacted by COVID-19 (travel restrictions, study site closed, patient chose not to attend site visit, renal biopsy not allowed at site requiring an extended randomized treatment period, patient received COVID-19 diagnosis, lack of study site personnel, lack of home nursing, local labs used instead of protocol-defined central labs and other). The data will be included in listings. Additionally, if a subject discontinued study treatment early or discontinued early from the study due to COVID-19, these data will be summarized as part of subject disposition. Local laboratory data collected due to COVID-19 will be listed.

Adjustments for missing data due to COVID-19 are incorporated into the multiple imputation analyses, completer analyses, per-protocol analyses and sensitivity analyses. Additionally, wider analysis windows are being allowed in order to capture critical data (e.g. renal biopsy data at Week 26 and Week 52) to reduce missing data. See Section 3.1.2 and Section 5 for additional details.

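### The Week 26 analysis windows have no stop at the switch to avacopan, so a post-switch value can be counted as the placebo-controlled result

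*SAP*

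**What the plan says.** SAP 3.1.2 takes scheduled visits as they are labelled in the EDC. Where one is missing it falls back on windows: "If a scheduled visit is not available, unscheduled and early termination visits will be assigned to analysis visits using analysis visit windows". The upper limit is set separately for each measure: "The end day of the analysis window will be calculated as the midpoint between the scheduled assessment and the next scheduled assessment for that parameter". Scheduled visits that fall outside their window are kept: "the scheduled study visit will be used in these cases". The printed table, offered as an example, gives Week 26 as Days 174 to 190 around a target of Day 183. SAP 3.1.8 adds that "wider analysis windows are being allowed in order to capture critical data (e.g. renal biopsy data at Week 26 and Week 52" are among the data to be captured in this way.

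On treatment, Protocol 3.2 states that after the double-blind period "the avacopan-matching placebo group will be switched over in a blinded manner to receive 30 mg avacopan". Protocol 6.11 places the first such dose at the Week 26 visit: "The patient will be asked to take the morning dose of avacopan while at the study center". That visit may fall within 7 days either side of Day 183.

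On the biopsy, Protocol 6.11 requires it "BEFORE patient is started on open-label treatment". SAP 2.2.5 repeats that it should be finished before avacopan starts, and SAP 5.2.1 describes the primary analysis as change to Week 26 within the double-blind period. The Time and Events Table schedules biopsies at screening, Week 26 and Week 52. Protocol 6.23 adds one on early withdrawal: "A follow-up renal biopsy will be performed if a patient is withdrawn early from the study".

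**The concern.** The window rule looks only at the spacing of assessments and ignores the change of treatment between them. For a parameter measured as rarely as renal histology, the midpoint after Week 26 lies deep in the period when every patient takes avacopan.

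Two routes lead to a wrong value:

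- **By window.** A placebo patient misses the Week 26 biopsy, enters Period B, and has an unscheduled or early-termination biopsy by the end of the window. The rule assigns it to Week 26.
- **By label.** A biopsy recorded as Week 26 in the EDC but taken after the first Period B dose is used without any check against that dose date.

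In either case an avacopan-treated biopsy stands as the placebo result in the primary endpoint. The same biopsy also feeds the chronicity index and the histologic response. Windows for the laboratory and quality-of-life endpoints have the same gap on a smaller scale.

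**Working it through.** **Inputs.** Target days (SAP 3.1.2 table): Week 23 = 162, Week 26 = 183, Week 28 = 197, Week 32 = 225, Week 52 = 365. Next scheduled assessment after Week 26: biopsy, Week 52 (Protocol Time and Events Table); UPCR, Week 28 (SAP 5.3.1); MCP-1, Week 28 (SAP 5.3.5); eGFR, Week 32 (SAP 5.3.2), or Week 28 if the protocol's serum chemistry schedule is used; SF-36/EQ-5D, Week 32 (SAP 5.3.6). Switch: the Week 26 visit, nominal Day 183, permitted range Days 176 to 190 (Protocol 6.11). Planning figures (SAP 9): 22 per arm, difference 35 points, SD 34.

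**Reproducing the printed window.** The lower midpoint is (162 + 183)/2 = 172.5, rounded up to 173 as the last day of Week 23, so Week 26 starts at Day 174. The upper midpoint is (183 + 197)/2 = 190. This gives Days 174 to 190, as printed.

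**Applying the same rule by parameter.** End day = (183 + next target day)/2.

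| Parameter | Window end | Days past switch at 183 | Switch at 176 | Switch at 190 |
|---|---|---|---|---|
| Biopsy | (183 + 365)/2 = 274 | 91 | 98 | 84 |
| eGFR (SAP 5.3.2), SF-36/EQ-5D | (183 + 225)/2 = 204 | 21 | 28 | 14 |
| UPCR, MCP-1 | (183 + 197)/2 = 190 | 7 | 14 | 0 |

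On the protocol's chemistry schedule the eGFR window would also end at Day 190.

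**Looking for a barrier.** The biopsy-before-avacopan statements say when to do the procedure, not how to assign a late value. The double-blind wording in SAP 5.2.1 states intent. The individual adjustments in SAP 3.1.2 are optional and concern visits that follow a late scheduled visit, not a missing one. The one explicit period barrier is in SAP 5.3.1.4, where carrying forward the last observation may not cross treatment periods. It governs that sensitivity analysis, not the windows.

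**Size per patient.** If one of 22 placebo patients shows the whole planned effect, the placebo mean moves by 35/22 = 1.6 points. The standard error of the difference is 34 × √(2/22) = 10.25, so this is about 1.6/10.25 = 0.16 standard errors.

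**Illustration.** The documents give no count of affected patients, so this range is an assumption. With k affected placebo patients, each showing a share g of the effect, the expected difference is 35 × (1 − k × g/22). Power is for a two-sided t test at 0.05 with SD 34 and 22 per arm.

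| k | g | Expected difference | Power |
|---|---|---|---|
| 0 | – | 35.0 | 91.5% |
| 1 | 0.25 | 34.6 | 90.9% |
| 2 | 1 | 31.8 | 85.8% |
| 4 | 1 | 28.6 | 77.9% |

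**The case against.** The strongest reply is that the route is narrow. Windows apply only when the scheduled value is missing. Protocol 4.4 allows withdrawal from the study only for withdrawn consent or loss to follow-up (Protocol 7.2.4.7 adds pregnancy). Such patients seldom provide a biopsy, and early-termination procedures are done only where possible. Patients who stop drug or fail treatment remain in the study and so create no early-termination biopsy. Blinded review before data freeze (SAP 8.1) may catch a case, and the per-protocol criteria consider excluding patients without a Week 26 biopsy. All this stands as to frequency, but none of it changes the value that the rule gives to the primary ITT analysis.

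Five stronger readings are tempting, and the documents do not support them:

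- *The SAP has abandoned the biopsy-before-avacopan requirement.* It has not: SAP 2.2.5 keeps it. The window algorithm merely fails to enforce it.
- *The printed Day 190 limit is itself a fault.* Day 190 is also the latest permitted Week 26 visit, so a value on Days 184 to 190 can be pre-switch.
- *The wider windows in SAP 3.1.8 are meant to admit post-switch biopsies.* The same section foresees randomized treatment being extended when a site cannot do the biopsy. A biopsy delayed in that way is still pre-switch.
- *The biopsy window opens at Day 92.* That treats Day 1 as the previous biopsy. The baseline biopsy is at screening or up to 12 weeks earlier. From Day −42 the midpoint is (−42 + 183)/2 = 70.5, and it is earlier still for older biopsies. The point does not depend on the start day.
- *This could produce a false positive.* Placebo patients counted after starting an effective drug pull the arms together, so no such risk is shown.

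**Conclusion.** The gap is real. As written, SAP 3.1.2 can place a value taken on open-label avacopan into the placebo-controlled Week 26 result: up to Day 274 by window for biopsy, and without any date limit for a biopsy labelled Week 26. That conflicts with the SAP's own statements on biopsy timing and on the double-blind period. It is therefore a rule that can return the wrong value for the primary endpoint, not just an omitted detail.

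The practical size is probably small. Few patients should be affected, and each affected placebo patient moves the placebo mean by at most about 1.6 points. That ceiling assumes 22 per arm and the full 35-point effect after roughly 13 weeks of drug at most, which is generous. If avacopan works, the effect is dilution and some loss of power. The correction is worth making because it touches the primary endpoint of a small trial and costs very little.

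**What to change.** Add to SAP 3.1.2: in both arms, no efficacy assessment taken after the patient's actual first Period B dose may be assigned to Week 26 or any earlier visit, whether it is scheduled, unscheduled or early-termination. Values taken before the dose on that day remain eligible, as do biopsies delayed while randomized treatment was extended. The limit must be the actual dose date, because a fixed Day 183 would discard valid late pre-switch values.

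An excluded biopsy leaves Week 26 missing and goes to the multiple imputation already planned in SAP 5.2.1. The other endpoints are left missing in the MMRM, which SAP 5.3.1.1 already runs without imputation.

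The cost is one sentence and one date comparison in programming. The downside is that a few observed values are set aside. They include some in the avacopan arm, where the drug does not change at the switch, and excluded biopsies would be replaced by imputation in a small stratum. A sensitivity analysis that includes the post-switch values would show whether this matters. SAP 1 allows such a revision before the database lock or snapshot.
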